9.2 SAMPLE SIZE DETERMINATION

Since we will collect data from the predictors [X], mediators [M] and outcomes [Y] at all three time points (baseline, 3 months, 6 months), we will use generalized linear mixed models to account for longitudinal repeated measurements over time to produce sample based inferential effects, which is a group-specific averaged effect size slope over all three time points to estimate each pathway strength.

For the power analyses, we proposed a small to medium effect size of 0.3 for our main outcome analyses without mediators. This was based on a combination of the effect size that is needed to detect what is reasonably thought to be a meaningful change and guidance from our pilot study. Thus, for the main effect we need a minimum of 107 subjects to reach 80% power at a significance level of 0.05. For the sequential mediation models, a sample of 120 provided at least 85% power at a significance level of 0.05. Thus, our target is to have a sample size of 120 to complete the intervention. However, if our attrition rate is higher than originally predicted, the sample size will be increased up to 150.

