9.4.8 TABULATION OF INDIVIDUAL PARTICIPANT DATA

9.4.9 EXPLORATORY ANALYSES

For qualitative data analysis, all sites will analyze de-identified data using Dedoose Software. These programs are approved for use by the NYU Langone IRB MCIT and Duke IRB IT. DUAs are in place to allow sharing of data between sites. Due to enrollment being less than anticipated, we plan to do mixed method analysis of the following aims:

- Exploratory Aim 1: Explore a detailed explanation of the impact of behavioral change techniques (BCTs) on oral hygiene behaviors and oral health outcomes (mixed method).
- Exploratory Aim 2: Examine relationship between the measures of adaptive leadership behaviors and the interventionist use of BCTS (mixed method).
- Exploratory Aim 3: Describe care partners' assessment of the intervention content and delivery (qualitative).

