*Target accrual: 120 dyads

Study Design

This is a three parallel arm randomized controlled trial (RCT) to evaluate the effectiveness of a care partner-assisted intervention to improve oral hygiene in individuals (≥ 60 years) with mild dementia. Participant-care-partner dyads were randomized into 1 of 3 groups: Treatment Group 1 (**TG1**), Treatment Group 2 (**TG2**), and the Control Group (**CG**) stratified by site. **TG1** and **TG2** were given smart electronic toothbrushes. Only **TG2** will receive in-home and telephone coaching throughout the duration of the study and were instructed to record daily brushing habits. The coaching sessions included individualized instruction on oral hygiene technique, cueing strategy development, or oral hygiene monitoring and coaching. **TG1** and **CG** did not receive coaching sessions. While randomization occurred at the dyad level (participant-care partner), primary study outcomes will be assessed at the participant level. The study duration was 6 months, including a 3 month intervention phase, in which coaching and educational modules were delivered, followed by a 3 month maintenance phase in which no coaching or educational modules were presented to participants. Data was collected by the study team at three visits: baseline, 3-months (end of active intervention phase), and 6-months (end of three-month maintenance phase). The primary endpoint is oral hygiene (plaque index, gingival index) at 3 months, with a secondary endpoint of 6 months to explore maintenance of intervention effects.

Study Aims

Aim 1: Evaluate the effectiveness of a care partner-assisted intervention to improve oral hygiene and oral hygiene behaviors in individuals with mild dementia.

Hypothesis 1a: Compared to CG, both T1 and T2 will result in improved oral hygiene as measured by reduced plaque index, and reduced gingival index, at 3 months.

Hypothesis 1b: T2 will have higher improvement than T1, relative to CG, in oral hygiene as measured by a greater reduction in plaque index, and gingival index, at 3 months.

Aim 2: Assess changes in mediating factors/process outcomes, including communication between the dyads, oral health knowledge, and self-efficacy for both participants and care partners to understand mechanisms of the intervention.

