General Approach: The overall goal of this study is to demonstrate the effectiveness of the two intervention strategies (TG1, TG2) against that of CG. The primary outcomes are plaque index, which is quantified as the proportion of sites with plaque deposits on at least less than 1/3 of crown, and gingival index, which is quantified as the proportion of sites with at least some mild inflammation. While the unit of randomization is at the dyad level, the primary outcomes will be evaluated at the individual level. As participants and care-partners contribute repeated measures (at baseline, 3 months and 6 months), we will use a linear mixed modeling approach for the analysis of the primary hypotheses, to account for correlation among repeated measures from the same individual. Analyses for all study outcomes will be conducted according to the intention-to-treat (ITT) principle, where all participants are analyzed according to the group in which they were randomized, irrespective of their receipt of allocated treatment. For our primary analysis we will conduct a

complete case analysis, thus excluding participants who are lost to follow up. As a sensitivity analysis, we will use the strategy of last-observation-carried-forward (LOCF) (thus assuming no change), to impute missing values for participants lost to follow up, if a monotone pattern is demonstrated in complete data. A strategy of LOCF is conservative in that it may bias results towards a null effect, but eliminates bias related to differential dropout, especially in the case where participants with no improvement are less likely to complete follow-up assessments. Statistical analyses will be performed in R version 4.4.0. All statistical tests will be two-sided, and a p-value of < 0.05 will be considered statistically significant.

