Statistical Analyses (Aim 1): To examine between-group differences in baseline characteristics and outcome variables, we will use Chi-square tests or Fisher's exact tests to analyze categorical variables and a one-way analysis of variance (ANOVA) for continuous variables. The effectiveness hypotheses will be analyzed using a linear mixed modeling framework with random effects. Specifically, longitudinal outcomes (e.g. plaque index) will be regressed on a treatment indicator, timepoint indicator, interaction of the two, and additional participant-specific covariates as needed. That is for the i^{th} person and t timepoint, $\text{Plaque}_{it} = \alpha_i + \beta_0 + \beta_1 \cdot \text{Site}_i + \beta_2 \cdot X_i + \beta_g \cdot \text{Group}_i + \beta_t \cdot \text{Time}_t + \beta_{gt} \cdot \text{Group}_i \times \text{Time}_t + \varepsilon_{it}$, where the terms represent the following: α_i person-specific random effects, β_0 overall mean plaque, β_1 site effects, X_i additional participant-specific covariates, β_g group effects, β_t time effects, and β_{gt} the interaction effect between group and time. Covariates determined a priori (including: baseline index scores, baseline functional status) will be included via the flexible X_i term. If data suggest a between-group difference (e.g. significant interaction between time and group) on the primary outcomes of interest, we will conduct the following pairwise comparisons using estimated means (**TG1 vs. CG**; **TG2 vs. CG**), at 3 months and 6 months. To control for multiple comparisons, pairwise comparisons will incorporate a False Discovery Rate-controlling procedure (e.g. Benjamini-Hochberg) which yields the desired type-I error rate of 5%. Lastly, depending on the distribution of the proportions for the primary outcomes (plaque, gingival indices) we may explore alternative distributions (e.g. beta regression) if it improves model fit. To address secondary outcomes including: 1) participants' frequency of toothbrushing, 2) participant's duration of toothbrushing, 3) participants frequency of interdental cleaning, 4) participant's interproximal cleaning technique, and 5) participants' oral hygiene skills score, and 6) participants' oral health knowledge score, we will use the same analytic approach outlined above consisting of linear mixed modeling with random effects. Given the overall sample size and number of secondary outcomes, all secondary outcome analyses will incorporate an appropriate False Discovery Rate-controlling procedure (e.g. Benjamini-Hochberg).

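### The 80% power in section 9.2 rests on 107 participants; the SAP records 54 to 60, restates no power or precision, and makes the 3-month contrasts with control conditional

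*Combined protocol and SAP*

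**What the plan says.** **Planned size.** Protocol section 9.2: "we proposed a small to medium effect size of 0.3 for our main outcome analyses without mediators"; "for the main effect we need a minimum of 107 subjects to reach 80% power at a significance level of 0.05"; "our target is to have a sample size of 120 to complete the intervention". The only change it foresees is an increase to 150. It does not state the metric of 0.3, the test, an SD, a within-person correlation or the predicted attrition.

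**Recorded size.** The SAP's sample-size table, as of 05/08/24, gives consented/completed as 20/18 (TG1), 20/17 (TG2), 20/19 (control) and 60/54 in total. The note beside it reads "Target accrual: 120 dyads". Protocol section 9.4.9 introduces its mixed-method aims with "Due to enrollment being less than anticipated".

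**Primary question.** The SAP (Study Design) places the primary endpoint at 3 months. Hypothesis 1a is that, relative to control, "both T1 and T2 will result in improved oral hygiene as measured by reduced plaque index, and reduced gingival index, at 3 months".

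**Primary analysis.** SAP General Approach: a "complete case analysis, thus excluding participants who are lost to follow up". Under Statistical Analyses (Aim 1), the TG1–control and TG2–control comparisons at 3 and 6 months are introduced by "If data suggest a between-group difference (e.g. significant interaction between time and group) on the primary outcomes of interest".

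**Where the SAP responds to sample size.** It cites sample size when choosing false-discovery-rate control for the secondary outcomes and when reducing mediation to exploratory single-mediator models. It has no corresponding statement for plaque or gingival index.

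**The concern.** Two gaps act together.

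First, the only power statement for the main outcome is the design-stage 80%. A reader could carry it over to a trial about half that size.

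Second, the comparisons that answer Hypothesis 1a depend on a prior signal in the data. The smaller the trial, the more often that signal fails to appear even when an effect of the planned size exists. The 3-month differences from control might then go unreported, just when a reader most needs an estimate and an interval to tell an uninformative result from evidence of no effect. Because the interaction is given only as an example of a trigger, the team may still report the contrasts, but nothing requires it. That leaves the choice to be made after the data are seen.

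**Working it through.** **1. The plan's own figure.** Read 0.3 as Cohen's f in a three-group, 2-df test at two-sided 0.05. The non-centrality needed for 80% power is 9.635 (large-sample chi-square), so N = 9.635 / 0.3² = 107.05. The exact F test gives 78.7% at 107. So 107 is not an arithmetic error, but this reading is an inference.

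**2. The shortfall.** 54/107 = 50%; 54/120 = 45%.

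**3. Power at the recorded numbers without choosing a metric.** Non-centrality is proportional to N. Take the value that gives 80% at 107 and multiply by N/107:

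| Test df | Non-centrality at 107 | Power at 54 | Power at 60 |
|---|---|---|---|
| 1 | 7.849 | 51.2% | 55.5% |
| 2 | 9.635 | 49.2% | 53.7% |
| 4 | 11.935 | 47.2% | 51.9% |

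Repeated-measures interaction tests tuned to about 80% at 107 give similar results. With f = 0.15 and correlation 0.41, power is 46.3% at 54 and 51.2% at 60. With f = 0.1225 and correlation 0.60, it is 45.6% and 50.4%. Overall: about 46–51% at 54 and 50–55% at 60.

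**4. With baseline adjustment.** The SAP includes the baseline index as a covariate. Assume f = 0.3 and baseline correlation r, replace f² by f²/(1 − r²), and use F with 2 and N − 4 df:

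| r (assumed) | N = 54 | N = 60 | N = 120 |
|---|---|---|---|
| 0.3 | 51% | 55% | 87% |
| 0.5 | 59% | 64% | 93% |
| 0.7 | 77% | 82% | 99% |

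**5. How often the SAP's example trigger fails.** Assume f = 0.3 at months 3 and 6, no difference at baseline, and compound symmetry with correlation ρ. The group-by-time test has 4 and 2(N − 3) df and non-centrality N × 0.09 × (2/3)/(1 − ρ). The chance of missing the effect is:

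| ρ (assumed) | N = 54 | N = 60 | N = 120 |
|---|---|---|---|
| 0.3 | 65% | 61% | 28% |
| 0.5 | 52% | 47% | 13% |
| 0.7 | 27% | 22% | 2% |

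The cost of the condition was also simulated with arms of 18/17/19 (TG1/TG2/control) and true improvements over control of 0.367 SD (TG1) and 0.735 SD (TG2), which give f = 0.3. A three-group F test at 3 months stood in for the trigger, with no false-discovery-rate step. Power for TG2 versus control was 57% without the condition and 44% with it.

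**6. Detectable difference and precision for each contrast.** Two-sided t test at 0.05, before the false-discovery-rate step. The detectable difference is at 80% power, and the half-width is t(0.975) × √(1/n₁ + 1/n₂). For 17 versus 19 this is 2.032 × 0.334 = 0.68 SD.

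| Arms | Detectable difference | 95% CI half-width |
|---|---|---|
| 17 v 19 (TG2 v control) | 0.96 SD | 0.68 SD |
| 18 v 19 (TG1 v control) | 0.95 SD | 0.67 SD |
| 20 v 20 (all consented) | 0.91 SD | 0.64 SD |
| 40 v 40 (planned) | 0.63 SD | 0.45 SD |

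Multiplying by √(1 − r²) for baseline adjustment at r = 0.3/0.5/0.7, the 17 v 19 contrast has a detectable difference of 0.92/0.83/0.69 SD and a half-width of 0.65/0.59/0.49 SD.

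**7. The relevant number is not given.** Protocol section 4.4 counts a participant as having completed only after the 6-month visit. If the SAP table uses that definition, the number with 3-month data lies between 54 and 60 on the dated count, and the split by arm is unknown.

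**8. Other outputs.** Table 3 of the SAP is titled for primary and secondary outcomes, but it is descriptive by arm and its variable list names neither index.

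**The case against.** The shortfall is open: the SAP prints the counts beside the target, and section 9.2 is correct as a design-stage calculation. That stands. What is missing is the consequence for the primary outcomes.

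Protocol section 9.4.1 plans group comparisons of the clinical outcomes without any condition, and the mixed model is fitted whatever its result. This is true, but those comparisons are three-group tests not tied to 3-month contrasts with control, and the SAP does not commit to reporting model coefficients. The contrasts are therefore not guaranteed rather than impossible.

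An overall test followed by pairwise comparisons is a common sequence, and protocol section 9.4.2 treats the interaction as the evidence of efficacy. That can justify conditioning the significance tests, but not withholding the estimates.

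The size of the problem depends on assumptions, and this stands. With r = 0.7, adjusted power is 77% at 54 and 82% at 60, close to the plan's 80%. The interaction calculation is not the test behind 107 and omits the baseline covariate. At ρ = 0.3 it misses 28% even at 120, so not all of that miss rate comes from the shortfall.

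The count is dated, and the documents do not expressly say that enrolment closed. The past-tense design text, the reference to available sample size under Aim 2 and section 9.4.9 all point to a final sample near this size, but that is an inference. The Table 3 omission looks clerical.

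**Conclusion.** The concern holds and should be fixed. The textual facts are firm: 80% power is tied to 107, the SAP records 54 to 60, no power or precision is restated for plaque or gingival index, and the Hypothesis 1a contrasts are conditional.

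On a test with 80% power at 107, power is roughly one half at the recorded numbers. Strong baseline adjustment could recover much of the loss, but the documents give no correlation to support relying on it. The trigger could often fail with a true effect of the planned size: a miss rate of 22–65% at 54 to 60 over the assumed correlations. With unadjusted intervals reaching about 0.68 SD either side of the TG2–control estimate (about 0.49 SD at r = 0.7), a non-significant result could not be read as no effect.

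The adjusted-power and interaction figures assume that 0.3 is Cohen's f. All correlations are assumed, and the recorded count is taken to be close to final.

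**What to change.** In the SAP:

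- State that the sample of 107 (target 120) behind the 80% figure was not attained.
- Give the detectable 3-month difference, or the power, for plaque and gingival index at the actual number per arm with 3-month data, with the SD scale, correlation and test assumed.
- Report TG1–control and TG2–control at 3 months for both indices as estimates with 95% confidence intervals, whatever the interaction p-value. Keep the false-discovery-rate step for the p-values.
- State that a non-significant result will not be read as no effect.
- List both indices among the Table 3 variables.

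The cost is a less favourable power statement and a few more lines of output from models already planned. No further participants and no new model are needed.

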9.3 POPULATIONS FOR ANALYSES

Per-Protocol analysis dataset will be described in the SAP.

9.4 STATISTICAL ANALYSES

9.4.1 GENERAL APPROACH

A statistical analysis plan (SAP) will be prepared and finalized prior to database lock and unblinding of participant's treatment assignment. This document will provide further details regarding the definition of analysis variables and analysis methodology to address all study objectives. A blinded data review will be conducted prior to unblinding of the participants' treatment assignments. This review will assess the accuracy and completeness of the study database, participant evalability, and appropriateness of the planned statistical methods. The SAP will not be posted publicly or registered before the study begins.

We will conduct data analysis in the following steps:

- Descriptive analysis on the sample characteristics, potential mediators, and oral hygiene behavioral and clinical outcomes. For the categorical variables, we will present percentages. For continuous variables, we will present means (with range and standard deviations).
- We will conduct ANOVA and Chi-Square analysis to compare group differences for the variables listed above. This will be based on two-tailed hypothesis testing. We will use p-value and 95% confidence interval for statistical significance test. P value of 0.05 will be considered the level of significance.
- We will use linear mixed models for continuous outcomes (e.g., plaque index, gingival index, oral hygiene skills, and duration of toothbrushing from smart toothbrush) accounting for within-participant correlation over time.
- We will use generalized linear mixed models for ordinal variables (e.g., self-reported duration of toothbrushing) accounting for within-participant correlation over time.
- Key covariates will be specified in the SAP.
- The tests for the underlying assumptions for the models will be specified in the SAP.

9.4.2 ANALYSIS OF THE PRIMARY ENDPOINT(S)

Details of the analysis of the primary endpoints will be provided in the SAP. A summary of the planned steps are provided here.

The first step will test whether the intervention is associated with differences across groups in the primary oral hygiene clinical outcomes. We will use linear mixed models for continuous outcomes (e.g., plaque index and gingival index) accounting for within-participant correlation over time. In addition to group, all models will be adjusted for site and time point and the interaction between group and time point – to assess whether group difference varied over time – as fixed effects; we will include a random effect for participants to handle within-participant clustering. Significant interaction between group and time point ($p < 0.05$) will provide statistical evidence for the efficacy of the intervention in improving oral health outcomes in Treatment Group 2 as compared to Treatment Group1 and the Control Group.

The subsequent steps will test the strength of the indirect effect of the intervention on oral hygiene clinical outcomes through mediators such as care partner factors and oral hygiene behavior outcomes. The following step will test the indirect effects are stronger than the direct intervention effects in Treatment Group 2 compared with Treatment Group 1 and the Control Group. The final step will test whether the impact of the intervention on oral hygiene clinical outcomes is sequentially mediated first by care partner's factors and then by oral hygiene behavioral outcomes.

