4.2 SCIENTIFIC RATIONALE FOR STUDY DESIGN

Our design includes three groups:

- Control Group participants will receive an educational booklet only and will continue their usual brushing techniques (manual or electric). They will receive a smart electronic toothbrush at the end of the study (at home visit 3)
- Treatment Group 1 participants will receive an educational booklet and 2 smart electronic toothbrushes.
- Treatment Group 2 participants will receive an educational booklet, 2 smart electronic toothbrushes, and in-home and telephone coaching.

In our pilot study, both the treatment (treatment group 2) and the comparison group (treatment group 1) improved in their oral hygiene outcomes. Thus, in the present study, we have added a usual care control group to address the possibility that the smart electronic toothbrush itself may serve as an intervention ingredient.

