6.3 MEASURES TO MINIMIZE BIAS: RANDOMIZATION AND BLINDING

The study team plans to take numerous steps to ensure a rigorous, unbiased study. Prior to the first visit, the statistician will be blinded when randomizing participant and care partner to study groups.

The procedures for the study visits differ based on which arm of the study a participant is assigned; thus, the research staff is not blind to the participant's assigned group. The randomization group determines which research staff members attend the home visits. The Research staff who conduct the study visits with participants and care partners will be trained to adhere to study procedures and interventions appropriately based on group assignment. The interventionist does not attend the visits for the Control Group and Treatment Group 1, reducing risk of contamination through delivery of in-person coaching. The participants will be recruited from local clinics and the intervention will be conducted at each participant's home, so the chances of contamination between the Treatment groups and the Control group is small.

Blinded randomization assignments will be determined by the statistician at the beginning of the study using a block (by sex) random allocation algorithm generated *a priori* by the statistician assuring there will be equal allocation to arms by site. Because the interventionist does not attend study visits for participants in the Control Group and Treatment Group 1, randomization must be done prior to the first visit.

This is a three-group randomized trial [Treatment Group 1, Treatment Group 2 and the Control Group] using randomization blocks by site to ensure balance within this potential confounder. Each randomization block will be composed of two units male and female in each treatment arm by site and randomization error will be minimized by ensuring that an equal number of all of units are randomized to each group. As minorities are recruited, they will sequentially be assigned to each group. To assess for randomization balance, we will use chi-square tests to examine if there are any statistically significant differences between race, and site by the three groups.

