9.4.3 ANALYSIS OF THE SECONDARY ENDPOINT(S)

The secondary endpoints are oral hygiene behavioral outcomes.

We will test whether the intervention is associated with differences across groups in the oral hygiene behavioral outcomes. We will use linear mixed models for continuous and ordinal outcomes accounting for within-participant correlation over time. In addition to group, all models will be adjusted for site and time point and the interaction between group and time point – to assess whether group difference varied over time – as fixed effects – and include a random effect for participants to handle within-participant clustering. Significant interaction between group and time point ($p < 0.05$) will provide statistical evidence for the efficacy of the intervention in improving oral health outcomes in Treatment Group 2 as compared to Treatment Group1 and the Control Group. Similar to the approach taken with the primary endpoints, we will then test the strength of the indirect effects of intervention on oral hygiene behavioral outcomes through mediators.

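### Protocol 9.4.2 and 9.4.3 read an undirected group-by-time interaction as evidence that Treatment Group 2 beats Treatment Group 1 and control, and the SAP lists no direct TG2 versus TG1 comparison to replace it

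*Combined protocol and SAP*

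**What the plan says.** Protocol 9.4.2 fits a linear mixed model with site, group, visit and group-by-visit terms. It explains the interaction as a term "to assess whether group difference varied over time". It then says that significance at the 0.05 level "will provide statistical evidence for the efficacy of the intervention in improving oral health outcomes in Treatment Group 2 as compared to Treatment Group1", with control as a second comparator. Protocol 9.4.3 draws the same conclusion for the behavioural endpoints: "will provide statistical evidence for the efficacy of the intervention in improving oral health outcomes in Treatment Group 2", again relative to both other arms. Neither section plans a TG2 versus TG1 contrast or a check of direction.

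Protocol 4.2 reports that both brush groups improved in the pilot, and that a usual-care arm was added "to address the possibility that the smart electronic toothbrush itself may serve as an intervention ingredient".

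The SAP (Statistical Analyses, Aim 1) treats a significant interaction as a sign that groups differ. It then compares TG1 with control and TG2 with control at 3 and 6 months, with false-discovery-rate (FDR) control. Its hypothesis 1b (Study Aims) is that TG2 improves more than TG1 at 3 months. No TG2 versus TG1 comparison is listed. On sidedness, the SAP's General Approach says: "All statistical tests will be two-sided, and a p-value of < 0.05 will be considered statistically significant".

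**The concern.** An omnibus interaction names no pair of arms and has no direction. It can be significant when the brush works and coaching adds nothing, when TG1 is the better arm, or when one arm deteriorates. The protocol nonetheless gives every such result one meaning: TG2 is efficacious against both other arms.

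At stake is the question the third arm was added to answer: whether any benefit comes from the brush or from care-partner coaching. Because the SAP has no contrast for hypothesis 1b, the protocol sentence is the only stated route to a claim that TG2 is better than TG1, and that route is invalid.

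**Working it through.** **Inputs from the documents.** Three arms (protocol 6.3: "This is a three-group randomized trial"), equal allocation, three visits, alpha 0.05, target 120 (40 per arm). The SAP's sample-size table gives 54 completers: TG1 18, TG2 17, control 19.

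**Inputs assumed.** Outcome SD 1, compound symmetry with within-person correlation ρ of 0.3 to 0.7, equal effects at 3 and 6 months, complete data, no covariates.

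**1. The plan's own figure.** Protocol 9.2 states "we proposed a small to medium effect size of 0.3 for our main outcome analyses without mediators" and "for the main effect we need a minimum of 107 subjects to reach 80% power at a significance level of 0.05". The metric of 0.3 is not named. Read as Cohen's f for a three-group test on 2 df, 80% power needs noncentrality 9.635 (large-sample chi-square), so N = 9.635 / 0.3² = 107.05. This matches 107 (108 if rounded up); the exact F test has 78.7% power at N = 107. The stated size therefore fits an omnibus three-group test, which does not single out TG2 versus TG1. If only the brush works, the group means are (0, −d, −d) and f = d√2/3, so f = 0.3 means d = 0.3 × 3/√2 = 0.64 SD with no coaching effect at all.

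**2. Degrees of freedom.** (3 − 1) × (3 − 1) = 4. For outcomes from the smart toothbrush, recorded only in TG1 and TG2, (2 − 1) × (3 − 1) = 2. That test does concern TG2 versus TG1, but it still has no direction.

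**3. How often the interaction is significant when coaching adds nothing.** Control means are (0, 0, 0) at the three visits; TG1 and TG2 means are both (0, −d, −d). The squared interaction effects sum to (2/3)(2/3)d² = 4d²/9. With n per arm, λ = n × (4d²/9) / (1 − ρ), and power comes from the noncentral F on 4 and 2(3n − 3) df. For d = 0.6, n = 40, ρ = 0.5: λ = 40 × 0.16 / 0.5 = 12.8, on 4 and 234 df, power 82%.

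| Brush-only effect | n per arm | ρ = 0.3 | ρ = 0.5 | ρ = 0.7 |
|---|---|---|---|---|
| 0.3 SD | 40 | 19% | 25% | 41% |
| 0.3 SD | 18 | 10% | 13% | 19% |
| 0.6 SD | 40 | 66% | 82% | 97% |
| 0.6 SD | 18 | 32% | 43% | 67% |

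A simulation of the 0.6 SD case agrees. In it, TG2 was significantly better than TG1 at 3 months in only 2% to 3% of runs.

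**4. Direction.** With TG1 truly better (0.6 SD against 0.3 SD, ρ = 0.5), the centred group effects have sum of squares 0.18. At n = 40, λ = 40 × 0.18 × (2/3) / 0.5 = 9.6, and the interaction is significant in 69% of trials; at n = 18, in 33%.

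**5. Hypothesis 1b.** It is phrased relative to control, but (TG2 − control) − (TG1 − control) = TG2 − TG1. Comparing the two effects against control is therefore the TG2 versus TG1 contrast. Two separate tests against control do not supply it: one significant and one not does not show that the two differ.

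**6. Power of the missing contrast.** Single time point, normal approximation: Φ(d / √(1/17 + 1/18) − 1.96). At d = 0.3: Φ(0.887 − 1.96) = 14%. At d = 0.6: Φ(1.774 − 1.96) = 43%.

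**The case against.** The strongest reply is that the operative plan does not apply this rule. Section 9.4.2 calls itself a summary and leaves the details to the SAP. The SAP does not repeat the inference; it uses the interaction as a gate and then estimates each treatment group against control. In a brush-only trial TG1 would usually beat control too, which would expose the brush effect. In simulation (0.6 SD, ρ = 0.5, unadjusted 3-month change contrasts after a significant interaction), TG2 alone beat control in about 9% of trials at 40 per arm and 7% to 8% at 18 per arm, far below the 82% and 43% at which the interaction is significant. This stands. A reader might infer that a brush-only effect would be reported as a coaching effect; the documents support only that it could be.

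A reader might also infer that the plan would credit TG2 when TG1 is better. That requires the analysts to ignore the fitted means, the direction stated in H1 (protocol 9.1) and the confidence intervals called for in 9.4.1. The step 4 figures show what the test cannot exclude, not what would be published.

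The rates are also fair game: neither the SD-scale effects nor the correlations come from the documents. Reading the plan's 0.3 as SD units gives the low rows of the table; reading it as Cohen's f gives about 0.64 SD, just beyond the high rows.

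What the reply does not meet is hypothesis 1b. The SAP lists no TG2 versus TG1 comparison and does not withdraw the protocol sentence, which a report could cite as prespecified support.

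**Conclusion.** The concern holds in a limited form. The interpretive sentence in 9.4.2 and 9.4.3 is wrong whatever values are assumed: an undirected interaction cannot show TG2 better than TG1 or better than control. The SAP's comparisons with control reduce the practical harm but leave hypothesis 1b without a valid test.

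The size is uncertain. With no coaching effect, the interaction is significant in about 19% to 97% of trials at 40 per arm and 10% to 67% at 18 per arm, over brush effects of 0.3 to 0.6 SD and correlations of 0.3 to 0.7. The achieved numbers, 17 to 19 completers per arm, are closest to the second range. These are rates at which the protocol's stated condition is met, not rates of false published claims. Given the SAP's gate and comparisons, this is a should-fix rather than a defect that invalidates the primary analysis.

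**What to change.** - **Protocol 9.4.2 and 9.4.3:** state that a significant interaction shows only that the arms' courses differ. Base any claim of TG2 efficacy on the signed 3-month TG2 minus control contrast, and any claim that coaching adds value on the signed 3-month TG2 minus TG1 contrast.
- **SAP, Statistical Analyses (Aim 1):** add TG2 versus TG1 to the pairwise list and to its FDR family, and tie it explicitly to hypothesis 1b.
- **Reporting:** give each contrast as an estimate with a 95% confidence interval.

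The contrasts come from the model already planned, and no new data are needed. The cost is one more comparison at each visit: 3 × 2 = 6 rather than 2 × 2 = 4 per outcome if the family is formed by outcome, which the SAP should state. Power for TG2 versus TG1 is low at 17 and 18 completers (about 14% at 0.3 SD and 43% at 0.6 SD, single time point). The SAP should therefore say that a non-significant result is not evidence that coaching adds nothing.
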